4.1 Overall Design

This is a phase 1b study assessing safety, tolerability, PK, pharmacodynamics, and efficacy of AMG 330 administered as clV infusion in combination with pembrolizumab in adult subjects with R/R AML.

The study is a non-randomized study and will consist of 2 sequential dosing cohorts. Both cohorts will include AMG 330 and pembrolizumab with the difference being the initiation date for pembrolizumab treatment.

This study will use a staggered enrollment approach. Subject enrollment will start with cohort 1 ([Section 4.1.1](#)). The first subject dosed in cohort 1 will serve as the sentinel subject. Subsequent subjects dosed in cohort 1 will start AMG 330 (█ µg/day) administration once sentinel subject has cleared the study day 21 dose (AMG 330 monotherapy at █ µg/day). Per sponsor determination, if the sentinel subject does not experience a dose-limiting toxicity (DLT) on days 15 to 21 after pembrolizumab is administered, the other subjects in cohort 1 will be allowed to continue the planned treatment schedule. If the sentinel subject experiences a DLT during days 15 to 21, the dose level review team (DLRT) will discuss the case and the decision will be made by the sponsor based on clinical assessments of the adverse event and potential decisions by the sponsor may include stopping AMG 330 and/or pembrolizumab, dose de-escalation of AMG 330, or continuing therapy at full dose. Investigators and sponsor will meet after all subjects in cohort 1 have completed study day 28 (ie, AMG 330 █ µg/day dose level in combination with pembrolizumab) to assess the safety profile. If pre-specified safety criteria are met (≤ 3 out of 10 treated subjects in cohort 1 experienced DLT by day 28), subjects enrolled in cohort 2 ([Section 4.1.2](#)) may proceed with the treatment schedule. Similar to cohort 1, the first subject dosed in cohort 2 will serve as the sentinel subject. Per sponsor determination, if the sentinel subject does not

experience a DLT during the first 7 days, the other subjects in cohort 2 will be allowed to continue the planned treatment schedule.

Safety data will be continuously monitored throughout the whole treatment period. Sponsor in consultation with investigators may reconvene to make appropriate safety measures and adjustments as needed.

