6.2 Dose Modification

6.2.1 Dose-cohort Study Escalation/De-escalation and Stopping Rules, Dose-Limiting Toxicities (DLTs)

Step Dose Level Determination

A decision to proceed with the next step dose of AMG 330 for each subject in cohorts 1 and 2 will be based on investigator's assessment of safety and upon approval by Sponsor.

In cohort 1, a sentinel subject will be treated first. The minimal interval between treatment start for the sentinel subject and other subjects in the cohort is 21 days. If the sentinel subject has not experienced a DLT by day 14 at █ µg/day AMG 330, he/she will proceed with 200 mg pembrolizumab on day 15 and remain at an AMG 330 dose level of █ µg/day for 7 days (until day 21). If the sentinel subject experiences a DLT during the first 7 days of treatment with AMG 330 at █ µg/day, this subject will be replaced, but the DLT will still be counted towards the study stopping rules. If the sentinel subject does not experience a DLT before or on day 21, the next subjects in the cohort may initiate dosing. If a sentinel subject experiences a DLT, the sponsor will issue a decision based on the evaluation of clinical significance of the adverse event by the DLRT and potential decisions by the sponsor may include stopping AMG 330 and/or pembrolizumab, dose de-escalation of AMG 330, or continuing therapy at full dose.

Cohort 2 will be initiated only after all subjects in cohort 1 completed study day 28 (ie, AMG 330 █ µg/day dose level in combination with pembrolizumab for 7 days), and if the rate of DLT is ≤ 3 out of 10 subjects. After receiving the DLRT recommendation, sponsor will render a final decision and will issue a written notification of the decision to investigators. Further information on dose level review meetings (DLRMs) is provided in [Section 11.3](#).

Individual Stopping Rules

Dosing for an individual will be stopped for any occurrence of a DLT. The event will be reviewed by the investigator and Sponsor for evidence of relationship to treatment and

clinical or medical significance to decide whether dosing may be resumed for the individual and any modifications to the dosing, if appropriate.

Dose Limiting Toxicities

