If a DLT occurs in a subject with clinical benefit from treatment, a restart at a lower dose can be considered if the toxicity has resolved to grade ≤ 1 and after consultation with the sponsor. If AMG 330 is discontinued, pembrolizumab may be continued as a monotherapy until disease progression for a maximum of 35 cycles (approximately 2 years) after discussion and agreement between the sponsor and the investigator. If pembrolizumab is discontinued, AMG 330 may be continued as a monotherapy.

Dose delay: treatment should be interrupted until the adverse event is resolved to grade ≤ 1 , and can then be resumed at the same dose unless the interruption lasted for more than 24 hours, please see below. (Note: if the event needs > 21 days to resolve, treatment has to be permanently discontinued, see also below).

Infusion Interruption

Significant events requiring a change in treatment will be managed by immediate infusion interruption:

- The subject experiences a DLT as defined in [Section 6.2.1](#)
- The subject experiences a clinically relevant grade 4 adverse event related to investigational product (see above) but does not meet the DLT criteria
- The subject meets criteria for discontinuation of investigational product as described in [Section 6.2.2](#)
- The subject experiences disease related adverse events and AMG 330 interruption is required for medical interventions
- Technical problem with the infusion pump
- The investigational product is incorrectly prepared or administered (eg, overdose)

Restarting the Infusion

Treatment may resume if the interruption is ≤ 21 days and if:

- The interruption occurred due to other reasons than toxicity (disease-related events, technical or logistic reasons; eg, diagnostic measurements). The infusion can be restarted at the same dose and without additional measures.
- The toxicity has resolved to CTCAE v5 grade ≤ 1 (in case of dose reduction, infusion may be re-started without prior resolution of the toxicity to CTCAE v5 grade ≤ 1 if the adverse event is not clinically relevant and upon discussion and agreement between the investigator and the sponsor)

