Dexamethasone (8 mg IV) should be administered within 1 hour prior to re-start and within 1 hour prior to each AMG 330 dose step(s). Dexamethasone is not required prior to the pembrolizumab administration unless it co-occurs with the AMG 330 step dose. In cases when administration of pembrolizumab co-occurs with AMG 330 step, pembrolizumab is administered first followed by dexamethasone followed by AMG 330. The subject should be hospitalized starting from re-start of infusion until 72 hours after the dose step. After each dose level increase, vital signs will be obtained as per the Schedule of Activities (see [Table 1-1](#), [Table 1-3](#), [Table 1-5](#)).

The number of days of exposure to both investigational products before and after an interruption should sum up to at least 70% of planned cumulative dose of AMG 330. In this case, the subject would still be DLT-evaluable. However, if the cycle was interrupted for more than 24 hours but less than 21 days, a new repeat cycle should be started and the interrupted cycle would not be evaluable for DLT, unless the event that lead to the interruption was a DLT.

Note: The end of infusion bone marrow assessment should be performed once it is confirmed that the cycle will not be resumed to assess treatment response. [REDACTED]

[REDACTED]

[REDACTED].

Permanent Discontinuation

A subject will permanently discontinue treatment with investigational product in the event of:

- Dose-limiting or other unmanageable toxicity. Exception: If a DLT occurs in a subject with a clear clinical benefit from treatment a restart at a lower dose can be considered if the toxicity has resolved and after consultation with the sponsor. This includes:
 - Grade 4 CRS
 - Grade 3 CRS occurring at the initial step dose for a cycle (ie, at the 10 µg/day)
 - Grade 2 or 3 CRS meeting any of the criteria listed below:
 - Grade 2 or 3 CRS that does not improve to ≤ grade 1 within 7 days
 - Grade 3 CRS that does not improve to ≤ grade 2 within 5 days
- Re-occurrence of the same grade 4 adverse event
- 3 infusion interruptions > 24 hours in cycle 1
- Disease progression as defined by 2017 European LeukemiaNet (ELN) criteria ([Döhner et al, 2017](#))
- Withdrawal of subject's consent to treatment
- Subject or investigator not compliant with the study protocol
- Occurrence or progression of a medical condition which in the opinion of the investigator should preclude further participation of the subject in the study

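### After a DLT in the cohort 1 sentinel, the protocol both allows full-dose continuation and requires permanent discontinuation with at most a lower-dose restart, and no section says which rule prevails

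*Protocol*

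**What the plan says.** The consequence of a DLT is set out in several places.

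- **Protocol 6.2.2.1, Permanent Discontinuation.** The list opens with "A subject will permanently discontinue treatment with investigational product in the event of", and its first item is dose-limiting or otherwise unmanageable toxicity. The only exception is "If a DLT occurs in a subject with a clear clinical benefit from treatment a restart at a lower dose can be considered", with the toxicity resolved and after sponsor consultation.
- **Protocol 6.2.2.1, Criteria for Dose Delay or Dose Reduction.** This has a similar exception in different terms. Clinical benefit need not be clear, and "a restart at a lower dose can be considered if the toxicity has resolved to grade" 1 or below.
- **Protocol 6.2.1, Individual Stopping Rules.** "Dosing for an individual will be stopped for any occurrence of a DLT". Investigator and sponsor then review the event "to decide whether dosing may be resumed for the individual and any modifications to the dosing, if appropriate".
- **Protocol 6.2.1, Step Dose Level Determination.** After a sentinel DLT the sponsor's options include "stopping AMG 330 and/or pembrolizumab, dose de-escalation of AMG 330, or continuing therapy at full dose". No study day limits this list.
- **Protocol 4.1, repeated in SAP 3.1.** For a sentinel DLT on days 15 to 21 the options again include "dose de-escalation of AMG 330, or continuing therapy at full dose".
- **Protocol 4.2.1.** A cohort 1 sentinel with a DLT in the first 14 days is DLT evaluable, does not go on to the combination, and hands the sentinel role to the next subject.
- **Protocol 6.2.2.1, Infusion Interruption and Restarting the Infusion.** A DLT is a listed reason for interruption. Treatment may resume if the interruption is at most 21 days and the toxicity is at grade 1 or below. After less than 24 hours, whatever the reason, the infusion restarts at the last dose level. After more than 24 hours, step doses lead back to the interrupted level. Neither rule makes an exception for DLTs.

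**The concern.** The sentinel is there to show early whether the combination is tolerable. If that subject has a DLT, the protocol should give one answer on what happens next. Here one section removes the subject from treatment, with a conditional lower-dose restart as the only way back. Two others allow the sponsor to leave the dose unchanged. Whoever applies one of these texts can be out of line with another.

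What is at stake is the subject's safety and the reading of data collected after the DLT. Adverse events and responses are summarised on the Safety Analysis Set (SAP 6.1, 9.5 and 9.6), which keeps the subject whatever dose follows. Cumulative exposure, later treatment-emergent events and later response would then depend on which section was applied.

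**Working it through.** The point is textual, so the main check sets the rules side by side.

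| Source | Who | Dosing after the DLT | Clinical benefit required? | Full dose possible? |
|---|---|---|---|---|
| 6.2.2.1 Permanent Discontinuation | any subject | discontinue; exception is a lower-dose restart | yes, clear | no |
| 6.2.2.1 Dose Delay or Reduction | any subject | lower-dose restart may be considered | yes | no |
| 6.2.1 Individual Stopping Rules | any subject | stop, review, possibly resume | not stated | not excluded |
| 6.2.2.1 Restarting the Infusion | any interrupted subject | same level (under 24 h) or steps back to the interrupted level (over 24 h) | not stated | not excluded |
| 6.2.1 Step Dose Level Determination | cohort 1 sentinel, any day | stop, de-escalate or continue | not stated | yes |
| 4.1 and SAP 3.1 | cohort 1 sentinel, days 15 to 21 | stop, de-escalate or continue | not stated | yes |
| 4.2.1 | cohort 1 sentinel, days 1 to 14 | no combination | not applicable | not with the combination |

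**Step 1, sentinel on days 15 to 21.** Take a constructed case: a DLT on day 18 that settles to grade 1 within 24 hours. Under 4.1 and 6.2.1 the sponsor may keep the full dose. Under the discontinuation list the subject stops, or restarts lower if benefit is clear. Assuming clear benefit does not remove the clash, because the exception still names only a lower dose.

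**Step 2, sentinel on days 1 to 14.** Section 4.2.1 ends progress to the combination. The list in 6.2.1 has no day limit, so on its face it still offers full-dose continuation.

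**Step 3, other subjects.** No text offers them full-dose continuation by name. The review in 6.2.1 can be read as applying the conditions in 6.2.2.1, but it does not refer to them. The restart rules cover interruptions caused by a DLT and lead back to the same or the interrupted level, which does not match a restart restricted to a lower dose.

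**Step 4, effect on the DLT analysis.** In 6.2.1 a subject who has had a DLT is evaluable on that ground alone, so later dosing changes neither membership of the DLT set (SAP 6.2) nor the subject-level count. The plan's own figures take that count as given, and they reproduce:

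- P(at least 1 DLT in 6 at a 25% rate) = 1 − 0.75^6 = 0.822 (stated 82%).
- P(at least 3 DLTs in 10 at rate p) = 1 − Σ C(10,x) p^x (1−p)^(10−x), summed over x = 0, 1, 2. At p = 10%, 20%, 30%, 40% and 50% this is 7.0%, 32.2%, 61.7%, 83.3% and 94.5% (stated 7%, 32%, 62%, 83% and 95%).

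**Step 5, how often the direct conflict could arise.** It needs a DLT in the sentinel. For one sentinel the chance of a DLT by day 28 is the DLT rate itself. The true rate is unknown. Over the 10% to 50% that section 9.4.1.1 considers, the expected number is 1 × 0.10 = 0.10 to 1 × 0.50 = 0.50 per sentinel. Days 15 to 21 are only part of that window, so their share cannot be larger.

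**The case against.** The strongest defence is that 6.2.1 gives the general process and 6.2.2.1 the conditions: stop, interrupt, review, then apply the benefit, resolution and lower-dose requirements. For subjects other than the sentinel this largely stands, since a review that decides whether dosing may resume does not waive conditions stated elsewhere. It does not rescue the sentinel text, because full dose cannot be a detail of a lower-dose-only exception.

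Section 6.2.2.1 also calls its criteria general guidelines. That sentence covers dose modifications and delays; the discontinuation list is worded as mandatory.

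The sponsor takes part in the post-DLT review, the lower-dose exception and the sentinel decision, so sites should not diverge on their own. That stands and limits the practical risk. It does not tell the sponsor which of its own texts governs.

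The sentinel options might be meant for the other cohort 1 subjects. They start only after the sentinel clears day 21, so continuing or de-escalating fits the sentinel more naturally, but the text does not say.

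Three stronger readings are tempting, and the documents do not support them:

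- **That any subject with a DLT may continue at full dose.** This option is written only for the cohort 1 sentinel. Sizing the conflict by applying a DLT rate to all 20 planned subjects therefore overstates it.
- **That days 15 to 21 are too early for clear clinical benefit.** The documents neither define that term nor give time-to-response data, and Step 1 does not need the premise.
- **That the primary DLT endpoint is undermined.** Step 4 shows that it is not directly affected.

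**Conclusion.** The point holds, and the plan is wrong as written. For a DLT in the cohort 1 sentinel, sections 4.1 and 6.2.1 and SAP 3.1 conflict with the Permanent Discontinuation list in 6.2.2.1, and section 4.2.1 adds a further outcome for days 1 to 14. For all other subjects the defect is weaker: the review and restart rules are not reconciled with the discontinuation rule.

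The direct conflict touches one sentinel at a time, or a successor if the role passes on. The consequences are for subject safety, exposure, and adverse events and responses after the DLT. The conclusion assumes that the sentinel options refer to the sentinel's own dosing. If they do not, the direct conflict falls away, but the text still has to say so.

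**What to change.** Reconcile protocol sections 4.1, 4.2.1, 6.2.1 and 6.2.2.1 (Dose Delay or Reduction, Infusion Interruption, Restarting the Infusion, Permanent Discontinuation) and SAP 3.1 into one stated consequence of a DLT that every section cites. In the same change:

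- say which section prevails if two differ;
- say whether the sentinel options concern the sentinel's own dosing or that of the other cohort 1 subjects, and on which study days they apply;
- use one wording for the benefit and resolution conditions;
- say whether the general restart rules apply to an interruption caused by a DLT.

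Which rule to adopt is for the sponsor's clinical team. The cost is wording in the next protocol amendment and a matching SAP edit. Sample size, the DLT definition and the DLT analysis need no change.

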6.2.2.2 Non-Amgen Investigational Product(s): Pembrolizumab

6.2.2.2.1 Dose Modification of Pembrolizumab if AMG 330 has been Interrupted

If toxicities due to AMG 330 do not resolve to grade ≤ 1 within 7 days of treatment interruption and supportive care as outlined, pembrolizumab may be postponed until both may be resumed per protocol. If AMG 330 is discontinued, pembrolizumab treatment may be continued following discussion and agreement between the investigator and Sponsor.

6.2.2.2.2 Dose Modification for Pembrolizumab

Adverse events associated with pembrolizumab exposure may represent an immune related response. These immune-related adverse events may occur shortly after the first dose or several months after the last dose of pembrolizumab treatment and may affect more than 1 body system simultaneously. Therefore, early recognition and initiation of treatment is critical to reduce complications. Based on existing clinical study data, most immune-related adverse events ensure adequate evaluation to confirm etiology or exclude other causes. Additional procedures or tests such as bronchoscopy, endoscopy, skin biopsy may be included as part of the evaluation. Dose modification and toxicity management guidelines for immune-related adverse events associated with pembrolizumab are provided in [Table 6-3](#).

Approved

Table 6-3. Dose Modification and Toxicity Management Guidelines for Immune-related Adverse Events Associated With Pembrolizumab

General instructions:				
irAEs	Toxicity grade (CTCAE V5.0)	Action with pembrolizumab	Corticosteroid and/or other therapies	Monitoring and follow-up
Pneumonitis	Grade 2	Withhold	Administer corticosteroids (initial dose of 1 - 2 mg/kg prednisone or equivalent) followed by taper Add prophylactic antibiotics for opportunistic infections	Monitor participants for signs and symptoms of pneumonitis Evaluate participants with suspected pneumonitis with radiographic imaging and initiate corticosteroid treatment
	Recurrent grade 2, grade 3 or 4	Permanently discontinue		
Diarrhea/Colitis	Grade 2 or 3	Withhold	Administer corticosteroids (initial dose of 1 - 2 mg/kg prednisone or equivalent) followed by taper	Monitor participants for signs and symptoms of enterocolitis (ie, diarrhea, abdominal pain, blood or mucus in stool with or without fever) and of bowel perforation (ie, peritoneal signs and ileus)
	Recurrent grade 3 or grade 4	Permanently discontinue		Participants with \geq grade 2 diarrhea suspecting colitis should consider GI consultation and performing endoscopy to rule out colitis Participants with diarrhea/colitis should be advised to drink

				liberal quantities of clear fluids. If sufficient oral fluid intake is not feasible, fluid and electrolytes should be substituted via IV infusion
AST or ALT elevation or Increased Bilirubin	Grade 2 ^a	Withhold	Administer corticosteroids (initial dose of 0.5 - 1 mg/kg prednisone or equivalent) followed by taper	Monitor with liver function tests (consider weekly or more frequently until liver enzyme value returned to baseline or is stable)
	Grade 3 ^b or 4 ^c	Permanently discontinue	Administer corticosteroids (initial dose of 1 - 2 mg/kg prednisone or equivalent) followed by taper	
Type 1 diabetes mellitus (T1DM) or hyperglycemia	New onset T1DM or Grade 3 or 4 hyperglycemia associated with evidence of β -cell failure	Withhold ^d	Initiate insulin replacement therapy for participants with T1DM Administer anti-hyperglycemic in participants with hyperglycemia	Monitor participants for hyperglycemia or other signs and symptoms of diabetes
Hypophysitis	Grade 2	Withhold	Administer corticosteroids and initiate hormonal replacements as clinically indicated	Monitor for signs and symptoms of hypophysitis (including hypopituitarism and adrenal insufficiency)
	Grade 3 or 4	Withhold or permanently discontinue ^d		
Hyperthyroidism	Grade 2	Continue	Treat with non-selective beta-blockers (eg, propranolol) or thionamides as appropriate	Monitor for signs and symptoms of thyroid disorders
	Grade 3 or 4	Withhold or permanently discontinue ^d		
Hypothyroidism	Grade 2, 3, 4	Continue	Initiate thyroid replacement hormones (eg, levothyroxine or liothyronine) per standard of care	Monitor for signs and symptoms of thyroid disorders
Nephritis: grading	Grade 2	Withhold		

according to increased creatinine or acute kidney injury	Grade 3 or 4	Permanently discontinue	Administer corticosteroids (prednisone 1 – 2 mg/kg or equivalent) followed by taper	Monitor changes of renal function
Myocarditis	Grade 1 or 2	Withhold	Based on severity of AE administer corticosteroids	Ensure adequate evaluation to confirm etiology and/or exclude other causes
	Grade 3 or 4	Permanently discontinue		
All other irAEs	Persistent grade 2	Withhold	Based on severity of AE administer corticosteroids	Ensure adequate evaluation to confirm etiology or exclude other causes
	Grade 3	Withhold or discontinue based on the event ^e		
	Recurrent grade 3 or grade 4	Permanently discontinue		

AE = adverse event; ALT = alanine aminotransferase; AST = aspartate aminotransferase; CTCAE = Common Terminology Criteria for Adverse Events; GI = gastrointestinal; irAE = immune-related adverse event; IV = intravenous; ULN = upper limit of normal
 
^a AST/ALT: > 3.0 - 5.0 x ULN if baseline normal; > 3.0 - 5.0 x baseline, if baseline abnormal; bilirubin: > 1.5 - 3.0 x ULN if baseline normal; > 1.5 - 3.0 x baseline if baseline abnormal
 
^b AST/ALT: > 5.0 to 20.0 x ULN, if baseline normal; > 5.0 - 20.0 x baseline, if baseline abnormal; bilirubin: > 3.0 - 10.0 x ULN if baseline normal; > 3.0 - 10.0 x baseline if baseline abnormal
 
^c AST/ALT: > 20.0 x ULN, if baseline normal; > 20.0 x baseline, if baseline abnormal; bilirubin: > 10.0 x ULN if baseline normal; > 10.0 x baseline if baseline abnormal
 
^d The decision to withhold or permanently discontinue pembrolizumab is at the discretion of the investigator or treating physician. If control achieved or ≤ grade 2, pembrolizumab may be resumed.
 
^e Events that require discontinuation include but are not limited to: Guillain-Barre Syndrome, encephalitis, Stevens-Johnson Syndrome and toxic epidermal necrolysis.
				

Pembrolizumab may cause severe or life-threatening infusion-reactions including severe hypersensitivity or anaphylaxis. Signs and symptoms usually develop during or shortly after drug infusion and generally resolve completely within 24 hours of completion of infusion ([Pembrolizumab Investigator's Brochure](#)). Dose modification and toxicity management guidelines on pembrolizumab associated infusion reaction are provided in [Table 6-4](#).

Table 6-4. Pembrolizumab Infusion Reaction Dose Modification and Treatment Guidelines

NCI CTCAE Grade	Treatment	Premedication at Subsequent Dosing
Grade 1 Mild reaction; infusion interruption not indicated; intervention not indicated	
 Increase monitoring of vital signs as medically indicated until the participant is deemed medically stable in the opinion of the investigator. 	None
Grade 2 Requires therapy or infusion interruption but responds promptly to symptomatic treatment (eg, antihistamines, NSAIDs, narcotics, IV fluids); prophylactic medications indicated for ≤ 24 hrs.	
 Stop Infusion. Additional appropriate medical therapy may include but is not limited to: 
 IV fluids Antihistamines NSAIDs Acetaminophen Narcotics Increase monitoring of vital signs as medically indicated until the participant is deemed medically stable in the opinion of the investigator. If symptoms resolve within 1 hour of stopping drug infusion, the infusion may be restarted at 50% of the original infusion rate (eg, from 100 mL/hr to 50 mL/hr). Otherwise dosing will be held until symptoms resolve and the participant should be premedicated for the next scheduled dose. 
Participants who develop grade 2 toxicity despite adequate premedication should be permanently discontinued from further study drug treatment
	Participant may be premedicated 1.5h (± 30 minutes) prior to infusion of pembrolizumab with: Diphenhydramine 50 mg po (or equivalent dose of antihistamine). Acetaminophen 500-1000 mg po (or equivalent dose of analgesic).
Grades 3 or 4 Grade 3: Prolonged (ie, not rapidly responsive to symptomatic medication and/or brief interruption of infusion); recurrence of symptoms following initial improvement; hospitalization indicated for other clinical sequelae (eg, renal impairment, pulmonary infiltrates) Grade 4: Life-threatening; pressor or ventilator support indicated	
 Stop Infusion. Additional appropriate medical therapy may include but is not limited to: 
 Epinephrine** IV fluids Antihistamines NSAIDs Acetaminophen Narcotics Oxygen Pressors Corticosteroids Increase monitoring of vital signs as medically indicated until the participant is deemed medically stable in the opinion of the investigator. Hospitalization may be indicated. 
**In cases of anaphylaxis, epinephrine should be used immediately.
 
Participant is permanently discontinued from further study drug treatment.
	No subsequent dosing
Appropriate resuscitation equipment should be available at the bedside and a physician readily available during the period of drug administration. For further information, please refer to the CTCAE v5.0 at http://ctep.cancer.gov		

CTCAE = Common Terminology Criteria for Adverse Events; IV = intravenous; NCI = National Cancer Institute; NSAID = non-steroidal anti-inflammatory drug

